1. A detectable increase in the (uptake) TBR of 18F-flotegatide in atherosclerotic plaque compared to the unaffected arterial wall.
2. An increase in TBR (18F-flotegatide uptake) in plaque that is implicated in the stroke or TIA compared to plaque that may be present in the contralateral carotid artery in symptomatic patients.
3. Most importantly, a detectable increase in atherosclerotic plaque uptake (TBR) of 18F-flotegatide in patients with stroke or TIA compared to 18F-flotegatide uptake in plaque in patients without symptoms of stroke or TIA.
4. A positive correlation between volume of lipid rich necrotic core and 18F-flotegatide uptake and a negative or lack of correlation between thickness of fibrous cap and 18F-flotegatide uptake.

Aim 2a and 2b.

1. Percent area of lipid rich necrotic core quantified from MOVATS staining may be positively correlated with TBR of the 18F-flotegatide uptake on PET imaging whereas, percent area stained for fibrous elements is expected to exhibit a negative correlation with 18F-flotegatide uptake.
2. We expect % area of plaque with CD68 (macrophage infiltration) and (or) CD31 staining (endothelial cell) to be higher among patients with increased 18F-flotegatide uptake relative to plaque from patients with lower levels of 18F-flotegatide uptake detected by PET imaging (**Figure 9**). Staining for α -smooth muscle actin may be increased in stable plaque with reduced 18F-flotegatide uptake. We also expect to find a strong correlation between area of staining with integrins α V β III, α 5 β 1 and 18F-flotegatide uptake.
2. We expect to find % area with macrophage staining and neovascular endothelial cell staining to be greater in plaque from patients with symptoms of stroke or TIA compared to plaque from those who are asymptomatic (**Figure 10**).
3. Ex-vivo binding studies: we expect 18F activity (PSL/mm²) of plaque sections measured by (autoradiography) in the absence of unlabeled RGD to be significantly greater than 18F activity in the presence of competing unlabeled RGD (Similar to **Figure 11**).

Feasibility***Aim 1.***

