The MRI protocol will consist of high- spatial resolution 3D imaging sequences in order to detect major vulnerable plaque features and minimize partial volume effects due to tortuous carotid arteries. The sequences will be: a) 3D MP-RAGE -a heavily T1- weighted imaging sequence for detection of intraplaque hemorrhage; b) 3D time-of-flight (TOF) for definition of luminal stenosis; and c) pre- and post-contrast T1-weighted 3D turbo spin echo (SPACE) to detect and quantify the lipid-rich necrotic core and fibrous cap. This will be followed by contrast injection (Gadolinium- DTPA, single dose 0.1 mmol/kg bodyweight, injection rate 2-3 cc/sec). Post-contrast SPACE will be acquired 5 minutes post injection. In addition, contrast-enhanced MRA may also be added into the protocol to obtain high- quality MRA. Typical imaging parameters are: 3D MP-RAGE axial acquisition, TR/TE = 15/3.5 msec, FOV = 160x160 mm², resolution = 0.6x0.6 mm², slice = 2 mm interpolated to 1 mm, flip angle = 15°, inversion time = 500 msec, turbo factor = 30. 3D TOF axial acquisition, TR/TE = 20/4.6 msec,

FOV = 160x160 mm², resolution = 0.6x0.6 mm², slice = 2 mm interpolated to 1 mm, flip angle = 20°. 3D SPACE coronal acquisition, TR/TE = 100/15 msec, FOV = 160x160 mm², resolution = 0.6x0.6 mm², slice = 0.6 mm, echo train = 50. Image quality review, processing (multi-planar reconstruction, MPR), and tissue characterization (outlining and size quantification) will be conducted on an image workstation with FDA-approved carotid plaque analysis software, MRI-Plaqueview (VPDiagnostics, Seattle, WA). From each of 3D sequences, contiguous cross-sectional slices that are perpendicular to the common carotid artery will be reconstructed. Intraplaque hemorrhage will be identified on 3D MP-RAGE as a hyper-intense area. Lipid rich necrotic core and fibrous cap will be identified on post-contrast 3D SPACE as hypo-intense and hyper-intense areas, respectively, with pre- contrast SPACE as reference. Vessel wall, lumen, and individual components will be outlined in a semi- automatic fashion. Their volumes will then be reported by the software.

Figure 1. Overall Experimental Scheme

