 - i. Symptomatic patients with plaque $\geq 70\%$ in at least one carotid artery that would be implicated as the source of embolus responsible for the stroke/TIA.
 - b. or to the vascular surgeon for CEA (Asymptomatic) with:
 - i. asymptomatic patients with a luminal stenosis of $\geq 70\%$ in at least one carotid artery (stable plaque) referred for CEA
 - ii. age-matched by deciles to symptomatic patients
 - c. or to the interventional cardiologist for evaluation and possible carotid stenting with:
 - i. asymptomatic patients with a luminal stenosis of $\geq 50\%$ in at least one carotid artery (stable plaque) referred for carotid stenting
 - ii. age-matched by deciles to symptomatic patients

Exclusion criteria:

1. stroke due to atrial fibrillation,
2. preexisting carotid stents in the artery of interest,
3. renal dysfunction defined as glomerular filtration rate $<40\text{ml/min}$,
4. allergy to gadolinium based contrast agents,
5. Volunteers who have had four or more prior previous gadolinium contrast scans
6. metal implants incompatible with MRI or other condition that prohibits MRI,
7. pregnancy,
8. allergy to animal dander or animal-instigated asthma
9. inability to provide informed consent and
10. age ≤ 18 years.

We propose to enroll a total of 6 patients over a period of 1 year.

Section 6.0**Treatment of Subjects**

All eligible subjects will undergo PET-MR of the neck (to image the bilateral carotid arteries) with 18F-Flotegatide within 96h of stroke or TIA and a simultaneous MRI and magnetic resonance angiography (MRA) of the carotid arteries for anatomic localization of the plaque

Plaque removed from asymptomatic patients at the time of CEA or carotid stenting (within 7d of PET-MR) will be used for histologic examination.

Section 7.0**Assessment of Efficacy**

Validation of the atherosclerotic plaque detected by PET-MRI using 18F-flotegatide will be completed via in-vivo PET imaging of patients with unstable carotid plaque. Plaque will be quantified by measuring the plaque uptake of 18F-flotegatide relative to 18F-flotegatide uptake in segments of the carotid vessel wall that are free of atherosclerosis.

Section 9.0.**Statistics**

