Image Analysis of plaque using MRI and MRA: Hemorrhage appears bright on MP-RAGE (**Figure 4**, panel A, yellow arrow). On contrast enhanced T1W images, fibrous portions of atherosclerotic plaque appear bright (**Figure 4** Panel B, arrowhead) and necrotic core in the plaque will be identified on the postcontrast T1W image as the area with no or slight contrast enhancement (**Figure 4** panel B yellow arrow). The percent stenosis will be quantified from TOF images (panel C, bright lumen is shown by the yellow arrow). Thickness of the fibrous cap and volume of lipid rich necrotic core will be quantified and plaque features including hemorrhage, and intact vs ruptured fibrous cap will be recorded.

Image Analysis of PET-MR: PET-MR images will be fused with the simultaneously acquired MR images. Coregistration of PET images with MRI will be performed using anatomic landmarks. Plaque is normally present in the carotid bifurcation and the proximal internal carotid artery. Plaque localized on the axial MR images will be correlated with PET signal. Uptake of 18F-flotegatide will be quantified in regions of interest (ROI) including both the vessel wall and the vessel lumen. The standard uptake value (SUV) in each slice position on the axial images will be quantified as SUVmean and SUVmax using commercially available software (MIM software Inc, Cleveland, OH). These are derived from the injected dose, time to acquisition to account for decay and patient weight. The SUVmax and SUVmean of unaffected segment of the carotid artery as well as the uptake of the tracer in the same level in the contralateral carotid artery will be quantified. SUVmean of the blood pool in the aortic arch will be quantified to derive background uptake. SUVmax of the target ROI is divided by the background SUVmean to derive a target to background ratio (TBR). The TBR of 18F-flotegatide in the plaque will be compared to TBR of unaffected vessel wall.

Comparison of morphologic markers of vulnerability with 18F-flotegatide uptake: MRI based plaque features including, volume of lipid core and thickness of fibrous cap will be directly compared to plaque uptake of 18F-flotegatide expressed as TBR from PET-MR images.

Sample Size and Power for Between Group Comparisons			Sample Size and Power for Correlation		
Effect Size	Number per Group	Power (1-β)	R	Number of Samples	Power (1-β)
1.16	19	80%	0.5	29	80%
1.16	25	90%	0.5	38	90%
1.2	13	80%	0.6	19	80%
1.2	17	90%	0.6	25	90%
1.25	9	80%	0.7	13	80%

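### Plaque TBR is compared with thin-wall TBR without any partial-volume step, so if uptake is above blood, geometry alone can make plaque read higher than unaffected wall

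*Combined protocol and SAP*

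**What the plan says.** Section 9.0, Image Analysis of PET-MR, sets the region of interest: "Uptake of 18F-flotegatide will be quantified in regions of interest (ROI) including both the vessel wall and the vessel lumen". The uptake measure follows: "SUVmax of the target ROI is divided by the background SUVmean to derive a target to background ratio (TBR"), with the background taken from blood in the aortic arch. The comparison is then stated: "The TBR of 18F-flotegatide in the plaque will be compared to TBR of unaffected vessel wall".

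The same contrast appears in three other places:
- Section 7.0 makes it the efficacy assessment, with the reference being "segments of the carotid vessel wall that are free of atherosclerosis".
- Section 3.0, Expected Results for Aim 1, item 1, anticipates "A detectable increase in the (uptake) TBR of 18F-flotegatide in atherosclerotic plaque compared to the unaffected arterial wall".
- Section 9.0, Statistical Analysis, makes it null hypothesis 1 and the basis of the statement that 17 per group gives 90% power for a 1.2-fold difference.

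On plaque size, Section 5.0 admits "Symptomatic patients with plaque $\geq 70\%$ in at least one carotid artery that would be implicated as the source of embolus", and by the stenting route "asymptomatic patients with a luminal stenosis of $\geq 50\%$ in at least one carotid artery (stable plaque) referred for carotid stenting". The enrolment text in Section 4.0 gives at least 70% for all asymptomatic patients.

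The PET processing described covers attenuation correction (Section 4.0) and decay, dose and weight (Section 9.0). Partial volume is mentioned once, in Section 4.0, as a reason for choosing high-resolution MRI sequences. The Aim 1 limitations do not raise it for PET. The MRI part of Section 4.0 does provide what a check would need: "Vessel wall, lumen, and individual components will be outlined in a semi- automatic fashion".

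**The concern.** PET blurs over several millimetres. A normal carotid wall is thinner than that, so its signal is averaged with the blood inside it and the tissue outside it. A plaque that narrows the artery by 50-70% or more is thicker and keeps more of its signal. The 0.70 mm PET voxel in Section 4.0 is a sampling interval, not a resolution, and does not remove the problem.

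TBR therefore depends on wall thickness as well as on tracer concentration. When tissue is hotter than blood, the thin wall is pulled down towards blood more than the plaque is. The plan compares two structures that differ in thickness by definition. A higher plaque TBR could then be read as extraction and retention by plaque when it reflects only the size of the structure. Section 3.0 (Future Directions) intends these results as preliminary data for a larger study, which would inherit the same measure.

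**Working it through.** **1. The plan's own figure.** The inputs are SD 0.3, significance level 0.05, 90% power and a 1.2-fold difference in two unpaired groups (Section 9.0, Figure 3). No reference TBR is given, so one has to be supplied. The formula is n per group = 2 × (1.96 + 1.28)² × 0.3² / difference².
- Reference TBR 1.7: difference 0.2 × 1.7 = 0.34, n = 16.4, rounded up to 17. This reproduces the plan.
- Reference TBR 1.0: difference 0.20, n = 47.3, rounded up to 48. This does not.

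The 1.2-fold effect is therefore the right yardstick, on a TBR scale of about 1.7.

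**2. Where the trial sits relative to blood.** The legend to Figure 10 (Section 3.0) gives plaque TBRs of 2.18 and 1.57, from PET-CT. Blood is 1 by construction. Under equal concentration, the wall would share the plaque's level.

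**3. Apparent ratio at equal concentration.** The inputs below are assumptions, not taken from the documents:
- PET resolution 4, 5 and 6 mm (Gaussian, full width at half maximum)
- normal artery with a 6 mm lumen and a 1 mm wall
- eccentric plaque with a 1.8 mm residual lumen and a 9 mm outer diameter
- surrounding tissue 0.5-1.0 times blood
- no noise

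Wall and plaque are given the same concentration C. The axial image is blurred and the maximum is taken inside the outer contour, as the plan's wall-plus-lumen region implies.

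| C (× blood) | Plaque/wall ratio, uniformly filled plaque |
|---|---|
| 1.5 | 1.25-1.39 |
| 2.0 | 1.45-1.70 |
| 2.5 | 1.63-1.93 |

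With an 8 mm outer diameter (no outward remodelling) the top of the overall range is 1.86 and the bottom 1.21.

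**4. Other wall and stenosis values.** These runs used a 0.7-1.5 mm wall, 50-70% diameter stenosis and surroundings 0.3-1.0 times blood:
- C = 1.2: 1.07-1.15
- C = 1.57: 1.18-1.42
- C = 2.0: 1.29-1.70
- C = 2.18: 1.33-1.80
- C = 1.0: 1.00 (wall 0.7-1.0 mm)
- C = 0.8: 0.84-0.98, reversed (wall 0.7-1.0 mm)

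**5. Plaque with an inert core.** A core of 2.2 mm radius holding 0.5 times blood was added to the step 3 geometry. Two runs gave 1.06-1.44 and 1.08-1.52 over C = 1.5-2.5. At C = 1.5 the first gave 1.06-1.12, below 1.2.

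**6. Consequence for null hypothesis 1 at 17 per group.** The rejection rate is approximately Φ(difference / (0.3 × √(2/17)) − 1.96). The differences come from step 4 (uniformly filled plaque).
- C = 1.57, difference 0.21: 0.21/0.103 = 2.04, rate 53%. Difference 0.42: rate 98%.
- C = 2.0, smallest difference 0.37: rate 95%.

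The nominal rate is 5%.

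**7. Whether a recovery-factor correction would work.** Recovery = (measured wall TBR − 1)/(C − 1). In the step 3 geometry the normal wall reads 0.96 at its lowest (C = 1.5), so recovery is −0.04/0.5 = −0.08. At its highest it reads 1.38 (C = 2.5), so recovery is 0.38/1.5 = 0.25. A divisor near or below zero is unusable.

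**The case against.** The best reply has four parts.

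*The effect is conditional and its size is assumed.* This stands. A reader might infer that plaque must always read higher than wall. The documents do not support that: the bias needs uptake above blood, and the true concentration in normal wall is not given. The target is on macrophages and neovessel endothelium, and the plan expects necrotic cores, so uniformly filled plaque is the less favourable model for the sponsor. With an inert core, the artefact need not reach 1.2-fold. Part of the preliminary results was also missing from the text reviewed.

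*The contrast that the plan ranks first is plaque against plaque.* This largely stands. Expected result 3 (symptomatic versus asymptomatic) compares thick with thick. In the runs, a 70% plaque read 2-6% hotter than a 50% plaque at fixed outer diameter, and up to 19% hotter under other geometries. That matters only if plaque size differs between groups, which the 50% stenting criterion in Section 5.0 permits and the 70% text in Section 4.0 does not.

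*The study is exploratory.* The formal tests are described as plans for a future study, and six patients will be read qualitatively. But a systematic bias affects a qualitative reading just as it affects a test.

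*Tracer binding does not rest on PET alone.* This stands. Aim 2b uses autoradiography of 20 µm sections with and without unlabelled RGD, which does not depend on PET resolution. It does not compare plaque with normal wall, however, so it does not rescue this contrast.

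**Conclusion.** The point holds for plaque versus unaffected wall, provided that uptake exceeds blood. On the stated assumptions, equal true concentrations give an apparent ratio of about 1.25-1.9 (uniform plaque) or about 1.1-1.5 (inert core), against a 1.2-fold target effect. The ratio is about 1 at blood level and below 1 beneath it. Expected result 1, null hypothesis 1 and the Section 7.0 assessment cannot by themselves establish selective uptake. The direction was consistent in every run at 1.2 times blood or more with uniformly filled plaque, and at 1.5 times or more with a core. The size depends on resolution, wall thickness and plaque composition, none of which the documents state.

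Two stronger readings should not be drawn. One is that the correlation between TBR and lipid-core volume is inflated because larger plaques read hotter. The documents do not say that core tissue holds tracer, and adding an inert core lowered plaque SUVmax from 1.81 to 1.36 times blood in one run (5 mm, C = 2.0, surroundings 0.5), so the direction is undetermined. The other is that the symptomatic versus asymptomatic contrast fails for the same reason. It is exposed only through unequal plaque size.

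**What to change.** In Section 9.0, Image Analysis of PET-MR:

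1. Tabulate maximum wall or plaque thickness, from the MRI outlines already produced, beside every TBR (plaque, unaffected wall and contralateral artery).
2. Add a sensitivity analysis. Take each patient's own wall and plaque outlines, assign them the same uniform uptake, and blur them over a stated range of scanner resolution, uptake and surrounding-tissue level. Report the plaque/wall ratio expected from geometry alone beside the observed ratio.
3. State that expected result 1 will be read as evidence of selective uptake only where the observed ratio exceeds that geometric range. Otherwise, report it as not distinguishable from a partial-volume effect. Carry the same wording into Section 7.0.
4. Do not decide the question by dividing the wall's excess over blood by a recovery factor, for the reason in step 7 of the working.
5. Reconcile the 50% and 70% stenosis criteria for asymptomatic patients between Sections 4.0 and 5.0.

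The cost is modest extra analysis of images already planned, with no new patient or scan. The drawbacks are dependence on an assumed resolution and a less favourable reading of expected result 1.

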This study will be conducted in accordance with Good Clinical Practice (GCP) requirements described in the current revision of International Conference on Harmonization of Technical Requirements of Pharmaceuticals for Human Use (ICH) Guidelines and all applicable regulations, including current United States Code of Federal Regulations (CFR), Title 21, Parts 11, 50, 54, 56, and 312 and Title 45, Part 164. Compliance with these regulations and guidelines also constitutes compliance with the ethical principles described in the current revision of the Declaration of Helsinki. This study will also be carried out in accordance with local legal requirements.

Section 12.0.**Data Handling and Recordkeeping**

Patients' names will remain confidential and will not be included in the database. Only patient number, patient initials, and birth date will be recorded in the data system. If the patient name appears on any other document collected (e.g., hospital discharge summary), the name will be obliterated before the document is transmitted. All study findings will be stored in paper CRFs. The patients will give explicit permission for representatives of the Sponsor, regulatory authorities, and the IRB/IEC to inspect their medical records to verify the information collected. Patients will be informed that all personal information made available for inspection will be handled in the strictest confidence and in accordance with all state, local, and federal data protection/privacy laws, including, without limitation, the HIPAA. All participants in the study will provide written authorization to disclose private health information either as a part of the written ICF or as a separate authorization form. The authorization will contain all required elements specified by 45 CFR 164 and ICH E6 as applicable, and will contain a waiver of patient access to study-related private health information until the conclusion of the clinical study. The authorization will remain valid and in full force and effect until the first to occur of (1) the expiration of 2 years after the study therapy is approved for the indication being studied, or (2) the expiration of 2 years after the research program is discontinued.

Individual patient medical information obtained during this study is confidential and its disclosure to third parties (other than those mentioned in this section) is strictly prohibited. In addition, medical information obtained during this study may be provided to the patient's personal physician or to other appropriate medical personnel when required in connection with the patient's continued health and welfare.

The study site will maintain a personal patient identification list (patient and treatment numbers with the corresponding patient names) to enable records to be identified.

In accordance with 21 CFR 312.62, an Investigator participating in this study shall retain records, including the CRFs and supporting data including signed and dated consent forms, and medical records, progress notes of the physician, the individual's hospital chart(s), and the nurses' and staff notes.

Section 13.0 FLOWCHART OF PROCEDURES

Procedures	Visit 1 ³ Baseline	Visit 2 (Pre-Operative PET Scan)	Follow-up Phone Call	Visit 3 (Surgical Day)
	(-28 days)	(-7 to 0 days)	(-4 - +3 Days)	Day 0
Standard of Care Procedures: Items, drugs and services that are part of regular care and would be done even if you did not take part in this research study. These will be billed to you and/or your insurance company.				
Medical History Review	X			
Medication Review	X	X	X	
Vital Signs x 3		X		
Physical Exam		X		
Electrocardiogram x 3		X	-	
Pre-op blood tests including Fasting lipid panels, C-reactive protein and HgBA1C1	X ¹	X ¹	-	
Pregnancy test, if applicable		X		
IV (intravenous) line inserted		X		
Carotid Endarterectomy or Stenting of Carotid Artery				X
MRI/MRA Imaging ²		X		
Research Related Procedures: Items and services done for research purposes only. These will NOT be billed to your insurance company.				
Subject Informed Consent	X			
Inclusion/Exclusion Criteria	X			
PET/MR ² Imaging with 18-flotegatilde		X		
Adverse Events	As they occur			
Sample of carotid artery plaque removed				X

¹If labs been collected within 30 days prior to the research imaging tests, no blood will be drawn to check your kidney function.

² Within 96 hours of stroke or TIA (if applicable; "Symptomatic" subjects only)

³ Baseline visit (Visit 1) may be combined with Visit 2.
